3.1.1.5. Part 1B – PF-06952229 in Combination With Enzalutamide in mCRPC

Part 1B is a dose-escalation of PF-06952229 in combination with enzalutamide conducted in patients who were previously treated for mCRPC. The starting dose of PF-06952229 will be based on safety, PK, and potential efficacy, but will not exceed the MTD or MAD of Part 1A. Because of the potential DDI between enzalutamide and PF-06952229, the maximum PF-06952229 dose for the combination may be higher than the monotherapy MTD, but not

higher than 800 mg BID. In addition to safety and tolerability, PF-06952229 PK exposure data may be reviewed for informed dose escalation. Based on evolving PK, PD and safety profiles, assessed in Part 1A, Part 1B may commence before reaching the MTD in Part 1A, and will follow an mTPI design as described in Section 3.1.1.4.

Enzalutamide (a CYP3A4 inducer) is predicted to decrease the PK of PF-06952229 (a CYP3A4 substrate) by 70% (Section 1.2.4). PF-06952229 is not expected to impact the PK of enzalutamide, therefore a fixed dose of enzalutamide is 160 mg QD, administered on a continuous basis. Dose modifications to enzalutamide will not be allowed during the DLT evaluation period.

3.1.2. Part 2 Dose Expansion

3.1.2.1. Part 2A – Single Agent PF-06952229 in mCRPC

PF-06952229 will be evaluated as a monotherapy in patients with mCRPC in this dose expansion cohort. An additional 10 patients will be enrolled to confirm the safety of the MTD determined in Part 1A (monotherapy dose escalation) and estimate the effect of antitumor activity of PF-06952229 as a monotherapy in patients with mCRPC.

3.1.2.2. Part 2B – PF-06952229 in Combination with Enzalutamide in mCRPC

PF-06952229 will be evaluated in combination with enzalutamide in patients with mCRPC in this dose expansion cohort. An additional 20 patients will be enrolled to confirm the safety of the MTD determined in Part 1B (combination dose escalation) and estimate the effect of anti-tumor activity of PF-06952229 in combination with enzalutamide in patients with mCRPC. Enzalutamide will be administered per the protocol.

3.2. DLT Definition

Severity of adverse events (AEs) will be graded according to CTCAE version 5.0. For the purposes of dose escalation, any of the following AEs occurring in the first cycle of treatment (within 28 days of first dose or until the patient completes the first cycle of therapy if there are treatment delays) which are clinically significant will be classified as DLTs, unless there is a clear alternative explanation and agreed upon by investigator and sponsor (eg, clearly and incontrovertibly due to underlying disease/progression or extraneous cause) where there has been a clinically significant change from baseline:

Clinically important or persistent toxicities that are not included in the criteria below
may be considered a DLT following review by Pfizer and the Investigators. All
DLTs need to represent a clinically significant shift from baseline.

Note: Labs must be repeated for confirmation. Only the lab result requiring confirmation must be repeated, not the entire panel.

Hematologic:

Any treatment-related hematologic laboratory abnormality specifically defined as:

- Thrombocytopenia Grade 4 for ≥7 days, or Grade 3 or 4 associated with ≥ Grade 2 clinically significant bleeding or requiring platelet transfusion (for bleeding events with no grading available clinically significant bleeding is defined as required hospitalization or urgent medical intervention);
- Neutropenia Grade 4 for ≥7 days; Grade ≥3 neutropenia with infection;
- Anemia Grade 4, or Grade 3 requiring blood transfusion.

Nonhematologic:

- Grade ≥3 toxicities that are considered clinically significant;
- Alanine aminotransferase (ALT)/aspartate aminotransferase (AST) >3x the upper limit of normal (ULN) with bilirubin >2x the ULN without another explanation (eg, cholestasis) will be considered a DLT, ie, confirmed drug induced liver injury (DILI) meeting Hy's law criteria;
- Grade 3 nausea, vomiting or diarrhea that does not resolve within 4 days despite maximal supportive therapy.

Nonhematologic and Non-Hepatic:

- Any toxicity causing greater than 2 weeks of dose delay is a DLT. Note: Patients deriving clinical benefit from study treatment who experience a DLT may continue on study at a reduced dose following recovery of the AE to Grade 0-1 or baseline, only after discussion between the investigator and sponsor;
- Any toxicity preventing patients from receiving 75% of study drug during the DLT evaluation period is a DLT.

The following AEs will not be adjudicated as DLTs:

- Any Grade 3 endocrinopathy that is adequately controlled by hormonal replacement;
- Grade 3 AE of tumor flare (defined as local pain, irritation, or rash localized at sites of known or suspected tumor);
- Any Grade 5 event clearly due to underlying disease or extraneous causes;
- Isolated Grade 3 laboratory abnormalities that are not associated with clinical sequelae and are corrected with supplementation/appropriate management within

72 hours of their onset at data cut off will not be taken into account for MTD determination including but not limited to:

- Grade ≥3 electrolyte abnormality lasting <72 hours, is not clinically complicated, and resolves spontaneously or responds to conventional medical interventions;
- Grade ≥3 amylase or lipase that is not associated with symptoms or clinical manifestations or pancreatitis.
- A patient is classified as DLT-evaluable if he/she experiences a DLT or if he/she otherwise in the absence of a DLT receives at least 75% of the planned doses of each investigational product and has received all scheduled safety assessments during the DLT window. If a patient fails to meet these criteria, he/she may be replaced.

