Visit Identifier (Visit Window) ^a	enrollment)	Day 1	Day 2	Day 7	Day 10 ^b	Day 15	Day 21°	Day 1	D ay 7		
Tumor markers PSA for prostate cancer ²⁰	X	X						X		X	
Other clinical assessments											
Serious and non-serious adverse event monitoring ²¹	X						◀▶	•			
Concomitant treatment(s) ²²	X						◀▶	•			
Survival Follow-Up ²⁵											X

Abbreviations: ◄--►= ongoing/continuous event; BID = twice daily; C = cycle; Day = D; ECG = electrocardiogram; ECOG = Eastern Cooperative Oncology Group; EOT = end of treatment; CT = computed tomography; MRI = magnetic resonance imaging; OS = overall survival; (X) = optional assessment.

- After Cycle 1, Day 1, tests and procedures should be done on schedule, but occasional changes by ±3 days (unless otherwise stated differently) are allowed for holidays, vacations and other administrative reasons.
- For Pharmacokinetics and additional sampling requirements, please see Pharmacokinetic, ECG, CCl Sampling Schedule for Part 1B Table below.
- a. Patients must maintain their original dosing schedule (7 days on, 7 days off) regardless of dose reductions or holds. To accommodate the dosing schedule, visit windows are not allowed into the "drug off" periods due to safety concerns; however, 2 day windows are allowed during the "drug on" period.
- b. Day 10 assessments are only performed in Cycle 2.
- c. Day 21 assessments are only performed in Cycle 1.

†Active Treatment Phase: Assessments should be performed prior to dosing on the visit day unless otherwise indicated. On mornings where patients are in the clinic, they will be instructed to hold their morning (or afternoon as applicable) dose, which will be administered by study staff onsite on clinic days. Acceptable time windows for performing each assessment are described in the column headers. One cycle consists of 28 days. Day 1 of any cycle visit should coincide with the day the PF-06952229 treatment begins. If there are delays due to toxicity, then the start of the next cycle visit may be delayed until the patient has recovered and can begin study treatment again. The active treatment phase is ongoing as long as the patient is receiving PF-06952229.

Study entry is Cycle 1 Day 1.

- 1. **Screening:** To be obtained within 28 days prior to study entry.
- 2. **Informed Consent:** Must be obtained prior to undergoing any study-specific procedures.

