- 3. **Medical/Oncologic History:** Includes history of disease process (eg, staging) (active or resolved) and concurrent illness. Includes prior treatments and any current medical treatments for any condition.

Protocol Activity	Screening	Active Treatment Phase†- One Cycle = 28 days								End of	Post-Treatme
	(≤28 days	Cycles 1 & 2 Cycles								Treatment/	nt
	prior to			•				•		Withdrawal ²³	Follow-Up ²⁴
Visit Identifier	enrollment)	Day 1	Day	Day	Day	Day	Day	Day	D		
(Visit Window) ^a	1	$\begin{array}{ c c c c c c c c c c c c c c c c c c c$							ay		
									7		

- 4. **Physical Examination:** Physical examinations (PEs) may be performed within 48 hours prior to a scheduled visit. A full physical examination is required at Screening and abbreviated PEs should be performed as appropriate at each visit where complete physical examinations are not required. For both full and abbreviated exams, patient should be assessed for evidence of bleeding (eg, bruising, petechiae, or hematomas). No need to repeat PE if baseline assessment is within 96 hours on Cycle 1 Day 1.
- 5. Baseline Signs & Symptoms: Patients will be asked about any signs and symptoms experienced within the 14 days prior to study entry.
- 6. **Vital Signs:** Includes temperature, sitting or semi-recumbent (same position must be used throughout the study and documented in source notes) blood pressure (BP), pulse rate (PR, to be recorded in the sitting position after 5 minutes of rest), and pulse oximetry (at rest and after exertion). On Day 1 of each cycle, vital signs should be measured prior to dosing (predose), BP, and PR will be repeated 1 hour after dosing. The time window for Vital Signs will match the allowable window for PK and ECGs.
- 7. ECOG Performance Status: Use Eastern Cooperative Oncology Group (ECOG) see Appendices.
- 8. **Hematology**: No need to repeat on Cycle 1 Day 1 (C1D1) if baseline assessment performed within 72 hours prior to that date. Assessments performed on Cycle 2 Day 1 (C2D1) and each subsequent cycle should be performed within 48 hours prior to dosing. See Assessments section for Laboratory Tests list.
- 9. **Blood Chemistry**: No need to repeat on C1D1 if baseline assessment performed within 7 days prior to that date (with the exception of serum creatinine which must be performed within 72 hours of C1D1). See Assessments section for Laboratory Tests list. Note that chemistries performed require serum phosphorus measurements.

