- 18. **Registration**: patient number and dose level allocation assigned by Pfizer Inc.

Protocol Activity	Screening		Active Treatment Phase†- One Cycle = 28 days								Post-Treatme
	(≤28 days		Cycles 1 & 2 Cycles 3+								nt
	prior to			•				·		Withdrawal ²³	Follow-Up ²⁴
Visit Identifier	enrollment)	Day 1	Day	Day	Day	Day	Day	Day	D		
(Visit Window) ^a	1		2	7	$10^{\rm b}$	15	21 ^c	1	ay		

- 19. **Study Treatment**: PF-06952229 will be administered orally for 7 days on, 7 days off, during a 28 day cycle. Day 1 safety laboratory tests must be reviewed by the Investigator prior to dosing at the beginning of each cycle for dosing confirmation. For Part 1B mCRPC patients will receive PF-06952229 in combination with enzalutamide. Patients will self dose as described above, with the exception of doses that will be administered on site. Patients must maintain their original dosing schedule regardless of dose reductions or holds. Patients will be required to return all bottles of PF-06952229 as well as the completed patient diary for drug accountability. On days of scheduled clinic visits, morning (AM) dosing should be undertaken in the clinic (ie, not at home).

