5.2. Patient Compliance

On PK clinic days, all doses of study treatments will be administered by the appropriately designated study staff at the investigational site.

Patients will be required to return all unused study treatment at the beginning of each cycle. The number of tablets/capsules returned by the patient will be counted, documented, and recorded.

On drug start and stop days, compliance telephone calls will occur for a minimum of the first 2 cycles to ensure compliance to the study drug schedule. Additionally, a patient diary will be provided to the patients to aid in patient compliance with the dosing instructions and used to support the accountability process. The diary will be maintained by the patient to include missed or changed doses (PF-06952229 and enzalutamide, where applicable). The number of PF-06952229 tablets remaining will be documented and recorded at each clinic visit or Day 1 of each cycle. The patient diary may also be used to support this part of the accountability process.

Enzalutamide will be administered in accordance with the protocol. All PF-06952229 and enzalutamide administration will be documented on the corresponding investigational product administration case report form (CRF). The information regarding diary completion, requirement to return all bottles and accountability documentation will also be performed on patients receiving enzalutamide (where applicable).

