5.4.6. Dose Delays

Re-treatment following treatment interruption for PF-06952229 treatment-related toxicity or at the start of any new cycle may not occur until all of the following parameters have been met:

- ANC $\ge 1,000 / \text{mm}^3$;
- Platelets count $\geq 50,000/\text{mm}^3$;
- Non-hematologic toxicities have returned to baseline or Grade ≤1 severity (or at the investigator's discretion, Grade ≤2 if not considered a safety risk for the patient).

If a treatment delay results from worsening of hematologic or biochemical parameters, the frequency of relevant blood tests should be increased as clinically indicated.

If these conditions are met within 4 weeks of treatment interruption, PF-06952229 may be resumed. Refer to the Dose Reductions section for AEs that require dose reduction at the time of treatment resumption.

If these conditions are not met, treatment resumption must be delayed for up to a maximum of an additional 2 weeks. If patients require discontinuation of PF-06952229 for more than 6 weeks at any time during the study, then study treatment should be permanently discontinued unless the investigator's benefit/risk assessment suggests otherwise after discussion with the sponsor's medical monitor or designee.

If a treatment interruption continues beyond Day 14 of the current cycle, then the day when treatment is restarted will be counted as Day 1 of the next cycle.

If patients require discontinuation of study drug for more than 4 weeks at any time during the study, then study treatment should be permanently discontinued, unless the investigator's benefit/risk assessment suggests otherwise and after discussion with the sponsor's medical monitor.

For enzalutamide, if a patient experiences $a \ge Grade\ 3$ toxicity or an intolerable side effect (at the PI's discretion), withhold dosing for 1 week or until symptoms improve to $\le Grade\ 2$, then resume at the same or a reduced dose (120 mg or 80 mg). Please contact Sponsor's medical monitor for any questions.

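### Minor: Part 1B schedules no safety laboratory tests between the pre-dose Day 15 draw and Cycle 2 Day 1, so the second dosing week of the DLT window has no end-of-course draw; using the existing Day 21 visit is a cheap, partial remedy

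*Protocol*

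**What the plan says.** - **DLT definition (Protocol Section 3.2; SAP Section 9.1).** The window is the first 28-day cycle. The laboratory-based criteria are Grade 4 neutropenia or thrombocytopenia lasting at least 7 days, transaminases above 3 times ULN with bilirubin above 2 times ULN, clinically significant non-hematologic toxicity of Grade 3 or higher, and in the protocol "Anemia Grade 4, or Grade 3 requiring blood transfusion". Laboratory findings must be repeated for confirmation.
- **Exclusions (same section).** "Isolated Grade 3 laboratory abnormalities that are not associated with clinical sequelae" are not DLTs if corrected within 72 hours. Uncomplicated electrolyte changes under 72 hours and asymptomatic amylase or lipase rises are also excluded.
- **Evaluability (same section).** A patient without a DLT is evaluable after at least 75% of planned doses if the patient "has received all scheduled safety assessments during the DLT window".
- **Part 1B Schedule of Activities.** Dosing is on Days 1-7 and 15-21. Hematology and chemistry are marked on Days 1, 7 and 15 of Cycles 1 and 2, and the Day 21 cells are blank. Assessments precede dosing by default. Footnote a allows 2-day windows while on drug. Footnote c says that "Day 21 assessments are only performed in Cycle 1". Footnote 8, on hematology, says "Assessments performed on Cycle 2 Day 1 (C2D1) and each subsequent cycle should be performed within 48 hours prior to dosing".
- **Part 1B PK/ECG schedule.** Cycle 1 Day 21 has an in-clinic dose, PK blood at seven time points and ECGs at three.
- **Safeguards.** Footnote 19 says "Day 1 safety laboratory tests must be reviewed by the Investigator prior to dosing at the beginning of each cycle". Section 5.2 says "compliance telephone calls will occur for a minimum of the first 2 cycles". If a delay follows worsening blood values, Section 5.4.6 says "the frequency of relevant blood tests should be increased as clinically indicated". Unplanned visits are left to the investigator.

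**The concern.** The two dosing weeks of Cycle 1 are not observed alike. The first has a draw on its last dosing day (Day 7) and another 8 days later (Day 15). The second has only the later draw, at C2D1. Both weeks lie in the DLT window.

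The evaluability rule does not reveal this, because it asks only whether the scheduled assessments were done. A patient with no blood test for most of the second half of the window satisfies it and enters the mTPI count as DLT-free.

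Two things are at stake. One is the care of a patient whose silent abnormality is found about a week late or not at all. The other is the dose decision: as with any missed DLT, one patient can move a cohort of three from staying to escalating. The liver is a nonclinical target organ (Sections 1.2.5 and 1.5.2.2), and Part 1B may go above the monotherapy MTD, up to 800 mg BID (Section 3.1.1.5).

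**Working it through.** **Inputs.** Draw days, dosing days and windows come from the Part 1B Schedule of Activities, with C2D1 as Day 29. DLT criteria come from Section 3.2 and decision cells from Table 2 in Section 3.1.1.4.

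**1. The plan's own figures.** With a Beta(1,1) prior and target interval 0.225-0.325, the unit probability mass is the posterior probability of an interval divided by its length. For n = 3:

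| DLTs | Under | Target | Over | Table 2 |
|---|---|---|---|---|
| 0 | 2.841 | 1.532 | 0.308 | E |
| 1 | 0.979 | 1.723 | 0.900 | S |

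The largest value in each row gives the Table 2 letter, so 1/3 is Stay and 0/3 is Escalate. The escalation-probability table in Section 9.2.2 also reproduces from (1-p)^3 + 3p(1-p)^5: 0.906 at p = 0.1 and 0.309 at p = 0.4, against the stated 0.91 and 0.31. That formula treats every DLT as observed. This point disputes neither figure.

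**2. Length of the gap.**
- Nominal: 29 - 15 = 14 days.
- C2D1 hematology drawn 48 hours early: 27 - 15 = 12 days.
- Day 15 draw also at the end of its 2-day window: 27 - 17 = 10 days.
- With a Day 21 draw, nominal days: 21 - 15 = 6, then 29 - 21 = 8. The Day 7 to Day 15 interval is also 8.
- Lead time over C2D1: 27 - 21 = 6 to 29 - 21 = 8 days.

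The 48-hour window is stated for hematology only.

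**3. Does a draw hit the episode?** Take an episode of L days on Days s to s+L-1, with onset s on Day 16 or later and ending by Day 28. It is missed if no draw falls inside it. Let C, the day of the C2D1 draw, be 27 / 28 / 29.

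| L | Possible start days | Missed now | Missed with Day 21 |
|---|---|---|---|
| 3 | 11 | 9 / 10 / 11 | 6 / 7 / 8 |
| 7 | 7 | 5 / 6 / 7 | 0 / 0 / 1 |
| 10 | 4 | 2 / 3 / 4 | 0 / 0 / 0 |

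If the Day 15 draw slips to Day 17 and onset is Day 18 or later, 7-day episodes are missed on 3 / 4 / 5 of 5 start days now and 0 / 0 / 1 with Day 21. These are counts of start days, not probabilities.

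**4. Does a hit establish the DLT?** For the cytopenia criteria the Grade 4 value must last at least 7 days, and after a normal Day 15 draw the onset date is unknown. Suppose, generously, daily draws from Day 21 on. The documented run is Days 21 to s+L-1, or s+L-21 days, and must be 7 or more. For L = 7 this needs s = 21 or later; for L = 10, s = 18 or later. Among episodes that C2D1 misses:

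| L | Hit by Day 21 | Documented as 7 days or more |
|---|---|---|
| 7 | 5 / 6 / 6 | 0 / 1 / 1 |
| 10 | 2 / 3 / 4 | 0 / 1 / 2 |

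So the large improvement in step 3 is in finding an abnormality. For these two criteria, little of it carries through to a documented DLT.

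**The case against.** **The anemia line is weak support.** Grade 3 anemia requiring transfusion is detected by definition, and Section 8.3 describes Grade 4 as life-threatening. This stands, so the case rests on the cytopenia, Hy's law and non-hematologic Grade 3 or higher criteria.

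**A hit is not a DLT.** A reader might infer from step 3 that a Day 21 draw would recover nearly all missed 7-day and 10-day cytopenia DLTs. Step 4 shows that it would not.

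**The chemistry case is narrow.** A DLT must be clinically significant. Under Section 8.2.2 an abnormal test is an adverse event only with symptoms, further testing or intervention, a change in dosing, or a judgment by the investigator or sponsor. Section 8.4.1 describes transaminases rising days or weeks before bilirubin, which makes a full Hy's law rise and recovery inside the gap less plausible. The Section 3.2 exclusions remove many brief events. All of this limits the point without removing it.

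**Safeguards exist.** The C2D1 review catches whatever persists. The others do not fill the gap: calls draw no blood, unplanned visits are discretionary, and increased testing follows a known abnormality.

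**No signal so far.** Appendix 10 reports no Grade 4 cytopenia among 20 Part 1A patients to 19 June 2020. That is relevant, but Part 1A has the same laboratory gap, so it is only partly reassuring.

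**Scope.** Part 2B has the same blank Day 21 cells, with that visit for at least its first 8 patients. The point is confined to Part 1B, where dose escalation is decided and the visit applies to every patient.

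**Conclusion.** The gap is real and can be read directly from the Part 1B schedule: 10 to 14 days without scheduled hematology or chemistry, covering nearly all of the second dosing week and the rest week after it. A silent abnormality meeting a laboratory criterion could resolve there unseen in a patient counted as DLT-free.

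This is a minor, low-cost monitoring improvement. The main benefits are detection of clinically significant Grade 3 or higher chemistry or hepatic changes and an earlier, dated start to follow-up of cytopenias. A reader might infer that the MTD is likely to be set too high. The documents do not support that: they give no rate for such events, one mistaken step does not fix the MTD because Section 3.3 requires at least 6 patients at that dose, and any effect on mTPI decisions is modest and unquantified.

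The day counts assume the nominal schedule, the stated windows, a fixed episode length and an episode ending by Day 28.

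**What to change.** In the Part 1B Schedule of Activities, mark hematology and blood chemistry, pre-dose, on the existing Cycle 1 Day 21 visit. No other rule needs to change: the tests then fall under the existing evaluability requirement, and an abnormal result leads to the repeat test that Section 3.2 already demands.

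Cost: one extra tube and local laboratory tests for about 20 patients, at a visit where blood is already taken. A DLT-free patient whose Day 21 sample is missed would no longer be evaluable and may need replacement.

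What remains: Day 22 to C2D1 stays without scheduled tests, 3-day events are helped only modestly, and Part 1A keeps the same gap because it has no Day 21 visit.

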9.1. Analysis Sets

1. Safety analysis set.

The safety analysis set includes all enrolled patients who receive at least one dose of study treatment.

2. Full analysis set.

The full analysis set includes all enrolled patients.

3. Per protocol analysis set (evaluable for MTD).

The per-protocol analysis set includes all enrolled patients who receive at least one dose of study treatment and who do not have major treatment deviations during the first cycle. Patients with major treatment deviations during the first cycle of treatment are not evaluable for the MTD assessment and will be replaced as needed to permit the MTD estimation. Major treatment deviations include the failure to satisfy major entry criteria (eg, confirmation of the target disease; signed informed consent) or use of other anticancer treatments during the active treatment period and disease follow-up phases other than as defined/allowed in this protocol. Major treatment deviations will also include:

- Administration of less than 70% of the planned number of doses of PF-06952229 (provided that the reduction in doses is not due to toxicity attributable to PF-06952229).
- Administration of more than 110% of the planned number of doses of PF-06952229.
- 4. Modified Intent to Treat (mITT) Population.

The modified intent to treat (mITT) is the analysis population that will follow the ITT principle and include patients receiving at least 1 dose of investigational product with baseline assessment and at least 1 post baseline assessment, disease progression, or death before the first tumor assessment. The mITT population will be used for analyses and to support conference presentations when the study is still ongoing.

5. PK analysis sets.

The PK parameter analysis population is defined as all enrolled patients treated who have sufficient information to estimate at least 1 of the PK parameters of interest. The PK concentration population is defined as all enrolled patients who are treated and have at least 1 analyte concentration.

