4.2. Safety Analysis Set

The safety analysis set includes all enrolled patients who receive at least one dose of study treatment.

4.3. 'PER PROTOCOL' Analysis Set (evaluable for MTD)

The per protocol analysis set includes all enrolled patients who receive at least one dose of study treatment and who do not have major treatment deviations during the first cycle.

Patients with major treatment deviations during the first cycle of treatment are not evaluable for the MTD assessment and will be replaced as needed to permit the MTD estimation.

Major treatment deviations include the failure to satisfy major entry criteria (eg, confirmation of the target disease; signed informed consent) or use of other anticancer treatments during the active treatment period and disease follow up phases other than as defined/allowed in this protocol. Major treatment deviations will also include:

- *Administration of less than 70% of the planned number of doses of PF-06952229 (provided that the reduction in doses is not due to toxicity attributable to PF-06952229).*
- *Administration of more than 110% of the planned number of doses of PF-06952229.*

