- Any toxicity preventing patients from receiving 75% of study drug during the DLT evaluation period is a DLT.

The following AEs will not be adjudicated as DLTs:

- Any Grade 3 endocrinopathy that is adequately controlled by hormonal replacement;
- Grade 3 AE of tumor flare (defined as local pain, irritation, or rash localized at sites of known or suspected tumor);
- Any Grade 5 event clearly due to underlying disease or extraneous causes;
- Isolated Grade 3 laboratory abnormalities that are not associated with clinical sequelae and are corrected with supplementation/appropriate management within 72 hours of their onset at data cut off will not be taken into account for MTD determination including but not limited to:
 - Grade ≥ 3 electrolyte abnormality lasting <72 hours, is not clinically complicated, and resolves spontaneously or responds to conventional medical interventions;
 - Grade ≥ 3 amylase or lipase that is not associated with symptoms or clinical manifestations or pancreatitis.
- A patient is classified as DLT-evaluable if he/she experiences a DLT or if he/she otherwise in the absence of a DLT receives at least 75% of the planned doses of each investigational product and has received all scheduled safety assessments during the DLT window. If a patient fails to meet these criteria, he/she may be replaced.

MTD Definition

A DLT rate of 27.5% with an equivalence interval of (22.5%, 32.5%) (note: provided the DLT rate for cardiac toxicity does not exceed 10%) will be utilized to estimate the MTD; patients will be enrolled in dose cohorts of 2-4 patients, and each patient will receive 2 courses of PF-06952229 (7 days on, 7 days off) in a 28 day cycle. Due to the discreteness of the dose levels and in the interest of the safety of patients, the estimated MTD is the highest tested dose level with DLT rate \leq approximately 32.5%. The dose finding decision will be based on a 1-cycle (28 day) DLT observation period.

At least 6 patients have been accumulated on a dose that can be predicted to be the MTD.

Recommended Phase 2 Dose (RP2D) Definition

The RP2D is the dose chosen for further investigation based on Phase 1 study results. If the MTD proves to be clinically feasible for long-term administration in a reasonable number of patients, then this dose usually becomes the RP2D. Further experience with the MTD may result in a RP2D dose lower than the MTD.

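### Two conflicting rules decide who is evaluable for the MTD (Protocol 3.2 and SAP 9.1 against Protocol 9.1 and SAP 4.3), so the DLT counts behind escalation and those reported need not match

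*Protocol*

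**What the plan says.** **Rule A: Protocol 3.2, repeated in SAP 9.1.** A patient who has a DLT is DLT-evaluable. Otherwise the patient is evaluable only if he or she "in the absence of a DLT receives at least 75% of the planned doses of each investigational product" and has all the safety assessments scheduled in the DLT window. On failure: "If a patient fails to meet these criteria, he/she may be replaced".

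**Rule B: Protocol 9.1, repeated in SAP 4.3.** This defines the Per Protocol set, whose title calls it evaluable for MTD. "Patients with major treatment deviations during the first cycle of treatment are not evaluable for the MTD assessment and will be replaced as needed". Major deviations include failing a major entry criterion, using other anticancer treatment, taking more than 110% of planned PF-06952229 doses, and "Administration of less than 70% of the planned number of doses of PF-06952229". The last has one exception: "provided that the reduction in doses is not due to toxicity attributable to PF-06952229".

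**Where each is used.** Protocol 3.1.1.4 requires at least three DLT-evaluable patients for an mTPI decision from Dose Level 5, which is Rule A's term. SAP 6.2.1 summarises DLTs by dose level in the Per Protocol set, which is Rule B.

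**The concern.** First-cycle DLT is a primary endpoint of Parts 1A and 1B, and Table 2 of the protocol takes two inputs: the number of DLTs and n. Both depend on who is evaluable. The two rules differ in cut-off, in the products counted, in whether safety assessments must be complete, and in whether a DLT by itself makes a patient evaluable.

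These are not just two analysis sets with separate purposes. Each rule carries its own replacement provision, and Rule B says its exclusions concern the MTD assessment. Document hierarchy does not settle the matter either. Section 9 of the protocol lets the SAP modify the protocol, but the SAP contains both rules.

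Cohorts have 2 to 4 patients (Protocol 3.3), so one patient's status matters. At stake is whether the reported DLT rate at a dose can be reconciled with the counts on which the dose was escalated, and whether a DLT can fall out of the primary summary.

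**Working it through.** **Check of Table 2.** Inputs are from Protocol 3.1.1.4 and 9.2: Beta(1,1) prior, target 0.275, interval (0.225, 0.325), exclusion threshold 0.95. For x DLTs in n patients the posterior is Beta(1+x, 1+n−x). The letter is that of the interval with the largest probability divided by its length (0.225, 0.100, 0.675).

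- 0/3, Beta(1,4): 0.6392/0.225 = 2.841; 0.1532/0.100 = 1.532; 0.2076/0.675 = 0.308. Largest is under-dosing: E, as printed.
- 1/3, Beta(2,3): 0.2203/0.225 = 0.979; 0.1723/0.100 = 1.723; 0.6074/0.675 = 0.900. Largest is the target interval: S, as printed. P(rate > 0.275) = 0.695, below 0.95, so the dose is not excluded.

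The same calculation matches every cell of Table 2 for 0 to 6 DLTs and n = 1 to 12.

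**Planned Cycle 1 doses.** PF-06952229 is given twice daily on Days 1–7 and 15–21.

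- Part 1A: 14 × 2 = 28.
- Part 1B: a single dose on Day 1 (Protocol 5.4.1), so 28 − 1 = 27.
- Enzalutamide, once daily: 28.

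| | 70% of plan | 75% of plan | Doses that pass B and fail A |
|---|---|---|---|
| Part 1A, PF-06952229 | 19.6 | 21 | 20/28 = 71.4% |
| Part 1B, PF-06952229 | 18.9 | 20.25 | 19/27 = 70.4%; 20/27 = 74.1% |
| Part 1B, enzalutamide | no rule in B | 21 | 20/28 = 71.4% or fewer |

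**The four differences.**

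(a) *Cut-off.* A patient without a DLT at one of the counts in the first two rows, for reasons other than toxicity, is in the Per Protocol set but is not DLT-evaluable. Take a cohort of three with no DLT and one such patient. Rule A leaves two, below the minimum of three, so a replacement is needed before an mTPI decision. After a clean replacement Rule A has 0/3 and Rule B has 0/4. Both read E; the reported denominator differs from the one used.

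(b) *Products.* A Part 1B patient with all PF-06952229 doses but at most 20 of 28 enzalutamide doses, missed for reasons other than toxicity, fails A. Rule B has no enzalutamide condition. Missed enzalutamide doses are not made up (Protocol 5.4.3), so the case can arise.

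(c) *Safety assessments.* Rule A requires all those scheduled in the window. Rule B does not mention them.

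(d) *Patients with a DLT.* Rule A always keeps them. Rule B excludes them and replaces them as needed in three situations:

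- dosing above 110% (28 × 1.10 = 30.8, so 31 or more doses; 27 × 1.10 = 29.7, so 30 or more);
- failure of a major entry criterion;
- PF-06952229 below 70% because of toxicity attributed to enzalutamide only, since the exception covers PF-06952229 toxicity alone. Protocol 5.4.7 asks that stopping PF-06952229 be considered before or together with enzalutamide, so both may stop.

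Take a cohort of three with one such DLT. Rule A gives 1/3 = S. Under Rule B the patient leaves, and after a clean replacement the summary shows 0/3. If the replacement also enters Rule A's count, that becomes 1/4, still S. The DLT is absent from the summary either way.

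**The case against.** **Only one rule is tied to the escalation decision.** Protocol 3.1.1.4 is the only text naming the patients for the mTPI decision, and it uses Rule A's term. This stands. A reader might infer that escalation itself would run on 0/3 = E in case (d). The documents do not support that: it follows only if the 9.1 set fed Table 2, and Rule B's label and replacement sentence leave the point unclear without saying so.

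**A DLT is not lost from the report.** Protocol 9.5.1 lists DLTs by dose level and SAP 6.2.1 adds a DLT listing. SAP 4.8 has the deviations that exclude patients from the per-protocol analysis fixed before database release and given in the study report. This stands. The loss is from the summary by dose, not from all reporting.

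**Most toxicity-driven shortfalls are handled alike.** "Any toxicity preventing patients from receiving 75% of study drug during the DLT evaluation period is a DLT", and a DLT makes the patient evaluable under Rule A. For non-hematologic, non-hepatic PF-06952229 toxicity both rules keep the patient. This stands, which is why (a) and (b) are limited to doses missed for other reasons. Protocol 3.1.1.5 also bars enzalutamide dose modification in the DLT window, which narrows (b).

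**Two further conflicts a reader might infer are not established.**

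- The 75% dose-loss criterion sits under a heading limited to non-hematologic and non-hepatic events, so a patient stopped by a cytopenia that is not a listed DLT might seem to be treated differently. After one clean replacement both rules give the same Table 2 letter. What remains is whether the event should be a DLT, which the evaluability rules do not decide, and an unlisted toxicity "may be considered a DLT following review by Pfizer and the Investigators".
- Protocol 3.1.1.3 allows discretion for patients who stop close to Day 28. PF-06952229 dosing ends on Day 21, so such a patient may already have every PF-06952229 dose, and no conflict is shown.

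**The cases are uncommon.** The gap in (a) is one dose count in Part 1A and two in Part 1B. The enzalutamide route in (d) needs confident attribution to one of two drugs started together, with PF-06952229 also below 70%. This is fair. It limits the size of the problem but does not remove the contradiction.

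**Conclusion.** The plan holds two incompatible definitions of evaluability for the MTD. One is used for the mTPI decision, the other for the primary DLT summary, and neither is given precedence. The firm consequence is that the DLT count and n behind a dose decision need not equal those reported for that dose.

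In (a), (b) and (c) the effect is on n and on who is replaced. In (d) a DLT leaves the primary summary: 1/3 becomes 0/3 after a clean replacement. The change of letter from S to E is conditional on a reading of 9.1 that no text states.

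The documents give no frequency for any of these cases. It is probably low, and no change in escalation probability is claimed. The dose counts assume the Cycle 1 schedule as written, with the single Day 1 dose in Part 1B. The point should be fixed because it touches a primary endpoint in very small cohorts and the correction is simple.

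**What to change.** Put one definition in Protocol 3.2 and 9.1 and in SAP 4.3 and 9.1:

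- a patient with a DLT is always evaluable;
- any other patient needs at least 75% of planned doses of each investigational product and all scheduled safety assessments in the DLT window.

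State that this same set is used for the mTPI decision, for replacement, for MTD estimation and for the DLT summary in SAP 6.2.1. If a separate per-protocol set is still wanted, drop its evaluable-for-MTD label and its replacement sentence.

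This changes wording only and needs no new data. The cost is occasionally one more patient at a dose, or a less favourable DLT count.
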